In the second project year we will scale up the peer educators and mobile phone technology to assess whether these interventions are sustainable, effective and appropriately cost effective. Qualitative studies will assess provider and patient attitudes towards these interventions.

Methods:

Study Design and Rationale

Research Design and Methods

Overview: A pilot peer educator/mobile phone intervention suggest that these programs are realistic in this resource-limited setting. However, there has been insufficient time and funding to assess the impact of these services on patient adherence and virologic outcomes. This proposal aims to build upon these early studies by:

- Extending the cluster-randomized peer educator and mobile phone programs for a one year study period in order to better assess impact on virologic treatment failure and adherence. Secondary outcomes include CD4 count changes, mortality, and morbidity...
- 2) If a positive impact is demonstrated during the first project year, we will scale-up the peer educator and mobile phone interventions to all communities in order to evaluate the effects on compliance and virologic outcomes after introduction of services, compared to the prior time period. These interventions will be further evaluated by an analysis of cost and sustainability.

Three Arm Cluster-Randomized Operations Research Study:

Study Design and Population: The program will continue with the current three armed randomization scheme of 6 clinics with peer educators but no mobile phones (Arm A), 4 clinics with peer educators and mobile phones (Arm B), and 5 clinics with no peer

educators. We will maintain a ratio of 15-20 patients per peer educator. New peer educators will be recruited and trained as necessary to maintain this patient ratio. Outcomes will be compared between clinic patients in the peer educator arms compared to the control arm, as well as between patients in clinics with peer educators equipped with mobile phones compared to clinics with peer educators without mobile phones, or the control condition. All analyses will use de-identified data. The study population will be ~1000 PEPFAR patients enrolled in the RHSP ART program by March, 2007. Process data will be collected on intervention implementation. Provider evaluations will be done via PEPFAR staff and peer educator surveys.

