1) Every six months, a questionnaire with a Likert scale (ordinal scale graded from 1 to 5, e.g 1=Strongly Agree, 5=Strongly disagree) and free text (unstructured response) questions will be administered to the PEPFAR staff and peer educators on their impressions of the intervention and suggestions for improvement. 2) Peer educators will be required to demonstrate knowledge and skills with an oral and practical test following bimonthly, one-day continuing education sessions. 3) RHSP field staff will perform spot checks of peer educator home visits during the initial 2 months of implementation. 4) Peer educator home visit forms will be entered into an electronic database and descriptive statistics compiled. This is an ongoing evaluation of personnel for QA/QC purposes.

Population:

Sample Size

The total number of PEPFAR patients expected to be enrolled by May 2007 is \sim 1000, so we anticipate \sim 330 patients in each of the three study arms. We already have \sim 6 months follow up information on \sim 800 patients in the pilot study. With a further one year follow up we will have information over \sim 18 months. Assuming a 5% drop out rate, we anticipate \sim 5,643 person months (\sim 470 py) per study arm. Detectable viral load (i.e., virologic failure) is \sim 28%. ¹²

Power Calculations or Statistical Plan

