This is an unmatched community randomized study. However, the Rakai communities have been selected to be homogeneous, and prior estimates indicate a coefficient of variation (k) between clusters of 0.24. Thus, design effects are modest (\sim 1.26). With a two-sided α = 0.05 and 1-β of 0.80, the study will have the power to detect a reduction in virologic failure in either intervention arm relative to the control arm with rate ratio (RR) \leq 0.70 (i.e., a failure rate ≤ 19.6%). If the two peer educator intervention arms are compared to the control arm, the study will have a power to detect a reduction in virologic failure of RR ≤ 0.74 (i.e. ≤ 20.7%). Descriptive analyses will compare patients in each study arm at time of enrollment with respect to sociodemographic characteristics, WHO stage, viral load, CD4 count and Karnofsky score. Univariate analyses will assess outcomes by strata of covariates in each intervention arm. For dichotomous outcomes (e.g., virologic failure, drug toxicity, OIs, and mortality) we will use multivariate log-binomial regression to estimate the relative risk of treatment failure, adherence etc. between intervention arms, adjusted for covariates found to differ between arms at p < 0.15 in univariate analyses, or suspected confounders. Adjustment for clustered data will use general estimating equations (GGE) to estimate robust variances. For continuous data (e.g., adherence percent, CD4 changes from baseline to follow-up, number of drug toxicity events) we will use tests and analysis of variance (ANOVA). The effects of peer educators and mobile phone interventions will be assessed by stratified analyses and by interaction terms. The number of treatment failures prevented will be estimated.

Inclusion and Exclusion Criteria

Inclusion in the study is determined by receipt of ARVs in the PEPFAR program. This protocol however deals only with the analysis of de-identified data and the intervention received by subjects takes place under a different service program.

Gender, Age and Locale

Both males and females between ages <1 and 60 are included.

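### The stated 80% power does not follow from about 330 patients per arm: at the protocol's own inputs it is about 60%, and the person-time figure credits every patient with 18 months.

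*Protocol*

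**What the plan says.** **Sample Size.** About 1000 patients are expected, hence about "330 patients in each of the three study arms". Roughly six months of follow-up already exist on about "800 patients in the pilot study". One further year and 5% dropout lead to "5,643 person months" (about 470 person-years) per arm. The baseline is given as a proportion: "Detectable viral load (i.e., virologic failure) is" about 28%.

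**Power Calculations or Statistical Plan.** "With a two-sided α = 0.05 and 1-β of 0.80", and a design effect of about 1.26, the study is said to detect a ratio of 0.70 or lower for either intervention arm against control ("i.e., a failure rate ≤ 19.6"%), and 0.74 or lower (20.7%) for both arms against control. The effect is called a rate ratio. The analysis is different: "we will use multivariate log-binomial regression to estimate the relative risk of treatment failure". The sample size and formula behind the power claim are not given.

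**Study Outcomes and Data Collection.** Virologic failure is a viral load above 400 copies/ml, and viral loads are taken every six months.

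**Study Design and Population.** The arms contain "6 clinics with peer educators but no mobile phones (Arm A), 4 clinics with peer educators and mobile phones (Arm B), and 5 clinics" in the control arm.

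**The concern.** A power claim for a binary outcome analysed as a relative risk depends on the number of patients. The Sample Size section ends in person-years, and the next section claims power without saying what was entered. If the claim cannot be recovered from about 330 patients per arm, the protocol promises more than it can deliver.

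Virologic failure is a primary outcome, and scale-up in the second year is conditional on a positive first-year result. A 40% chance of missing the planned effect, where the protocol states 20%, could lead to a wrong decision not to scale up.

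**Working it through.** **Inputs (all from the protocol).** Control failure p0 = 0.28; p1 = 0.28 × 0.70 = 0.196; both arms combined p1 = 0.28 × 0.74 = 0.2072; two-sided alpha 0.05 (z = 1.960); power 0.80 (z = 0.842); design effect (DE) 1.26; 330 patients per arm; 5% dropout, leaving 330 × 0.95 = 313.5. The 1.26 is taken as given.

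**1. The plan's person-time.** 330 × 18 × 0.95 = 5,643 person-months, and 5,643 / 12 = 470 person-years. The match is exact, so every patient was credited with 18 months. With 800 patients at 18 months and 200 at 12:

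(800 × 18 + 200 × 12) / 3 × 0.95 = 5,600 × 0.95 = 5,320 person-months = 443 person-years per average arm.

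**2. Power for one arm against control.** Power = Φ(|p0 − p1| / SE − 1.960), where SE² = DE × [p0(1 − p0)/n0 + p1(1 − p1)/n1]. Here p0(1 − p0) = 0.2016 and p1(1 − p1) = 0.1576.

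- 330 per arm: SE = 0.0370; 0.084 / 0.0370 = 2.268; Φ(0.308) = 62%.
- 313.5 per arm: SE = 0.0380; 0.084 / 0.0380 = 2.211; Φ(0.251) = 60%.
- Using the pooled variance under the null gives 61.7% and 59.5%, so the formula hardly matters.
- With no design effect at all, 330 per arm gives 72%.
- The ratio detectable with 80% power is about 0.63, before or after dropout.

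**3. Both arms against control at 0.74, after dropout (627 v 313.5).** p1(1 − p1) = 0.1643; SE = 0.0338; 0.0728 / 0.0338 = 2.156; Φ(0.196) = 58%. The pooled formula gives 60%. The detectable ratio is about 0.67.

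**4. Patients needed for the stated 80% at 0.70.** The pooled-variance formula needs 403 per arm before the design effect; 403 × 1.26 = 508.

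**5. Routes that might explain the claim.**

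| Entered in the calculation | Power at 0.70 | Detectable ratios (one arm; both arms) |
|---|---|---|
| 470 as patients per arm, DE 1.26 | 77% | 0.69; about 0.73 |
| 500 per arm (1500 / 3), DE 1.26 | 79% | 0.698; 0.738 |
| 470 person-years as a Poisson rate, DE 1.26 | 65% | 0.65; 0.68 |
| 313.5 per arm, one-sided 0.05, no DE | 80% | 0.699; 0.738 |

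For the Poisson row: SE² = 1.26 × (0.28 + 0.196) / 470, so SE = 0.0357; 0.084 / 0.0357 = 2.352; Φ(0.392) = 65%. Without the design effect it is 75%.

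**6. Sensitivity case: unequal arms.** If the clinics were of equal size (an assumption), 950 retained patients would split 6:4:5 into 380, 253 and 317. Power at 0.70 would be 64% for Arm A against control and 55-56% for Arm B against control, depending on the variance formula.

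**The case against.** **The mechanism is not stated.** A reader might infer that 470 person-years were entered as 470 independent patients. The documents do not support that as a fact. The route gives 77%, not 80%, and others fit at least as well. Five hundred per arm, from the projection of more than 1500 patients by the end of 2007 in the Gender, Age and Locale section, rounds to both stated ratios. A one-sided test without a design effect does too, although it contradicts the stated test and design effect. None of these is documented, and the study population is fixed at about 1000 under both Study Design and Population and Recruitment Process. So the mechanism falls, but the shortfall stands.

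**Longer follow-up can add information.** Viral loads are six-monthly, and generalised estimating equations can use repeated values. Three values on 313.5 patients give an effective size of 313.5 × 3 / (1 + 2ρ). With an assumed within-patient correlation ρ of 0.5 this is 470 and power is 77%; with 0.3 it is 588 and 86%; with 0.9 it is 336 and about 63%. It would therefore be too strong to say that follow-up time adds nothing. But the protocol invokes estimating equations only for clustering, and gives no repeated-measures basis and no correlation.

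**Unequal clinic numbers do not prove unequal arms.** Patients per clinic are not given, and the protocol expects about 330 per arm. A reader might infer that power in the phone arm is 55-56%; this is a sensitivity case only.

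**The remaining points are small.** The person-time error is about 6% (5,643 v 5,320) and does not drive power when each patient is counted once. The term rate ratio is glossed with 19.6% against 28%, so it reads as loose wording for a risk ratio, not as evidence of a time-based plan. Which viral-load visit to analyse, and whether to analyse mortality or morbidity as rates, can be left to a statistical analysis plan.

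**Conclusion.** The point holds as a failure of the stated power to follow from the stated population. At the protocol's own 28%, two-sided 0.05 and design effect of 1.26, about 330 patients per arm give about 62% power at a ratio of 0.70, and 60% after dropout. Both arms against control at 0.74 have about 58-60% after dropout. The detectable ratios are about 0.63 and 0.67 where the protocol states 0.70 and 0.74. This rests on equal arms, as the protocol expects, and on counting each patient once, which is the natural reading of a relative risk for a binary outcome when no repeated-measures basis is given.

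Separately, the person-time contradicts the follow-up described in the same paragraph and should be about 5,320 person-months (443 person-years) per average arm. How the 80% was obtained cannot be determined from the protocol.

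**What to change.** - Restate power and detectable ratios on the number of patients with a viral load, using actual patient counts in each arm after dropout, and name the sample size and formula used.
- If repeated six-monthly viral loads are meant to supply the extra information, say so and state the number of values per patient and the assumed within-patient correlation.
- Correct the person-time to about 5,320 person-months (443 person-years) per average arm, if it is kept.
- Call the effect a risk ratio, to match the log-binomial analysis.

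The cost is protocol wording and a short recalculation. No extra patients are needed; the stated figures become less favourable.

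### Enrolment and baseline are not tied to the start of an intervention that was already running, which leaves CD4 change and the viral-load covariate poorly anchored

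*Protocol*

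**What the plan says.** The protocol builds on an intervention already in place. The section on the three-arm study states: "The program will continue with the current three armed randomization scheme", with 6, 4 and 5 clinics. The Sample Size section adds: "We already have \sim 6 months follow up information on \sim 800 patients in the pilot study". It then counts that period towards the total: "With a further one year follow up we will have information over \sim 18 months".

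The Power Calculations or Statistical Plan section will "compare patients in each study arm at time of enrollment with respect to sociodemographic characteristics, WHO stage, viral load, CD4 count and Karnofsky score". Its log-binomial model for dichotomous outcomes is "adjusted for covariates found to differ between arms at p < 0.15 in univariate analyses, or suspected confounders". Continuous outcomes, including "CD4 changes from baseline to follow-up", are to be analysed with tests and ANOVA. The Study Outcomes paragraph also lists CD4 change from baseline as a secondary outcome.

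No section says whether enrolment means entry to the ART programme, to the pilot or to the new study year. No section ties baseline to the date on which a clinic's assigned arm was put into effect.

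**The concern.** When randomisation and first measurement coincide, enrolment is a clear anchor. Here they need not coincide: patients may have joined the ART programme before the pilot, during it or after it. Two things depend on the anchor.

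- **CD4 change.** If baseline lies well before the intervention, the change includes recovery on ART that the intervention could not have influenced.
- **Covariates for the primary virologic comparison.** A viral load from long before the intervention says little about who was suppressed when it began. A viral load from after it began is an early reading of the outcome itself, and adjusting for it takes out part of the effect under test. The larger the early effect, the more likely the p < 0.15 rule is to bring that covariate in.

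**Working it through.** **1. Where the pilot months sit.** The Sample Size section gives about 330 patients per arm, 18 months, 5% dropout and 5,643 person-months (about 470 person-years).

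- 330 × 18 × 0.95 = 5,643 person-months; 5,643 / 12 = 470.25 person-years. The plan's figure reproduces exactly.
- Follow-up starting after the pilot: 330 × 12 × 0.95 = 3,762.
- 18 months for the 800 pilot patients and 12 for the other 200: (800 × 18 + 200 × 12) × 0.95 / 3 = 5,320 per arm.

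The plan therefore treats the pilot's 6 months as follow-up. A baseline set after the pilot would fall inside that follow-up.

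**2. What enrolment most likely means.** Where the protocol spells the word out (the three-arm study section and Recruitment Process), it means enrolment in the ART programme. The Data Collection paragraph starts the questionnaires and descriptive data, including WHO stage and Karnofsky score, at ART initiation. Against this, the Aim places the trial in the first project year and the Methods overview speaks of a one-year study period, so entry to the new study year is not excluded.

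**3. The gap if enrolment means the ART programme.** ART provision began in June 2004. The population is fixed by March 2007.

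- June 2004 to March 2007 = 33 months.
- The protocol gives no pilot start date. Assuming about 6 months before the cut-off, the largest gap is 33 − 6 = 27 months. With the May 2007 date in the Sample Size section it is 35 − 6 = 29.

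This is the maximum, for the earliest patients. The documents do not give the distribution of ART start dates, so the typical gap cannot be computed.

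**4. How many patients had a peer educator in the pilot.** The background gives 19 peer educators with 15-20 patients each, 9 of them with phones.

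- With a peer educator: 19 × 15 = 285 to 19 × 20 = 380.
- With a phone-equipped peer educator: 9 × 15 = 135 to 9 × 20 = 180.

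So the roughly 800 patients with pilot follow-up include many who had no peer educator.

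**5. Effect of adjustment if enrolment means the new study year (illustration).** Failure is 28% in control and 19.6% under intervention (RR 0.70, the plan's target), both 6 months into the intervention and at the end. Failure is a threshold on a latent normal variable. The within-patient latent correlation is not in the documents and is assumed at 0.2 to 0.8. Simulated Mantel-Haenszel RRs are:

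| Latent correlation | Unadjusted RR | Adjusted for pre-intervention status | Adjusted for month-6 status |
|---|---|---|---|
| 0.2 | 0.693 | 0.693 | 0.719 |
| 0.4 | 0.703 | 0.704 | 0.764 |
| 0.6 | 0.696 | 0.696 | 0.798 |
| 0.8 | 0.701 | 0.701 | 0.853 |

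A pre-intervention covariate leaves the RR where it was. A month-6 covariate moves it towards 1.

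**The case against.** The strongest reply is that the protocol does not fix a wrong baseline. Its own use of the word points to enrolment in the ART programme. Those values precede exposure for patients already on ART when the intervention began, and are essentially pre-exposure for later starters. Adjusting for them conditions on nothing the intervention has changed. CD4 recovery from before the intervention is balanced between arms in expectation under randomisation, and CD4 change is only secondary. Viral load and CD4 enter the model only if they differ at p < 0.15 or are suspected confounders. The exact baseline window is ordinarily left to the SAP.

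Most of this stands, and it rules out three stronger readings that a reader might infer:

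- **That baseline is taken about 6 months into the intervention.** No section says so, and the wording and the person-time both lean the other way.
- **That the interventions had already run in about 800 of the 1,000 patients.** The 800 are patients with pilot follow-up; about 285-380 had a peer educator.
- **That adjustment would remove the effect.** An adjusted RR of 1.00 arises if the intervention is assumed to do all its work by month 6 and nothing afterwards. That result is built into the assumption. With a continuing effect, the illustration shows attenuation.

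Two points remain. Balance in expectation is weak protection with 15 clinics in three arms: time on ART can differ by chance, and an unadjusted ANOVA of CD4 change does nothing about it. And the section does more than stay silent. It names the time point, the covariates and the trigger for adjustment, and that time point is ambiguous because the randomisation was already live.

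**Conclusion.** The point holds in a limited form. On the better-supported reading the cost is precision: baseline may precede the intervention by up to about 27 months for the earliest patients (assuming a pilot start about 6 months before March 2007), CD4 change carries pre-intervention recovery, chance imbalance in time on ART goes uncorrected, and viral load at ART start is a weak covariate. The size of the CD4 effect cannot be worked out from the document. Systematic bias in the virologic comparison arises only on the less-supported reading and only if the adjustment is triggered; the illustrative shift is then from RR 0.70 to about 0.72-0.85, resting on the assumed correlations and on the full effect being present by month 6. This is a cheap improvement that also closes off the biased reading. It is not a must-fix.

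**What to change.** In the Power Calculations or Statistical Plan section, replace the reference to enrolment with a definition along these lines:

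- For patients on ART when their clinic's assigned arm was implemented, baseline is the last value on or before that date. For control clinics, use a single pre-specified reference date matched to implementation in the intervention clinics.
- For patients starting ART later, baseline is the last pre-ART value.
- Use this baseline for the arm comparison, covariate adjustment and CD4 change. Use no value measured after a patient's own baseline date as a covariate.
- Analyse CD4 change with baseline CD4 and time on ART at baseline as covariates, and with the same adjustment for clustering as the other outcomes.

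The cost is wording, plus recording each clinic's implementation date. The values come from routine monitoring (viral load every six months; CD4 every three months for one year, then every six). The downside is that some baseline values will be up to about 6 months old.

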Please note all patient records are routinely collected for clinical care so no additional consent is required and there is no risk to patients entailed by the evaluation, since deidentified data will be used.

Study Outcomes: The primary outcomes will be virologic failure (defined as viral load >400 copies/ml), and ARV adherence as measured by pill counts percentage (sum of ARV pills taken/sum of ARV pills prescribed). Secondary outcomes include change in CD4 count from baseline, morbidity (new opportunistic infection or drug toxicity), and mortality. These outcomes are recorded in clinical records and will be abstracted, and stripped of identifiers for analysis.

Data Collection: Patient Data: As part of the clinical service, viral loads are assessed every six months and CD4 counts every three months for one year, and then every six months thereafter through PEPFAR clinical monitoring and a parallel NIH funded R01 study to evaluate the ARV effects on HIV epidemiology and behaviors (1R01HD050180; PI [name]). Data on ARV adherence will be derived from peer educator home visit records and pill counts at the bi-weekly clinic visits as part of the routine clinical service. Morbidity outcomes and descriptive data (gender, age, WHO stage, Karnofsky score) will be collected through clinic records and questionnaires administered by ARV clinic staff to patients initiating ART, weekly for the first month, and then at 3, 6, 9, 12, and 24 months on ART. These are routinely collected data and do not add a research burden. Mortality data will be collected through verbal autopsy interviews with relatives and friends of deceased patients. This is routinely done as part of the Rakai cohort study. Mobile phone data will be captured in real-time with an automated, preprogrammed SMS system. This mobile phone intervention will use locally available phones and technology.

Additional operational evaluation procedures for Peer Educators:

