The rural Rakai district in southwestern Uganda has an estimated population of ~460,000 persons in an area of over ~5000 square kilometers. In June 2004, with PEPFAR funding, antiretroviral therapy was provided through a community-based mobile clinic program operating in 15 localities. Each clinic has a catchment area of several villages, and the mobile clinic visits each location once every two weeks. Between visits to the mobile clinics, patients are supported by a "treatment companion" who is a friend or relative selected by the patient to assist in treatment support. The program has ~1000 active patients on ART with ongoing recruitment and a projected >1500 patients by the end of 2007. The ART program also has a central clinic staffed by physicians during the weekdays, but it is difficult for many patients to expeditiously reach this clinic when urgent issues arise.

Rev. 11/07

Procedures:

Recruitment Process

Population will be ~1000 PEPFAR patients enrolled in the RHSP ART program by March, 2007.

Study Procedures in Sequential Order

See Mobile Phone Intervention Description below

Methods of Intervention

Peer Educator Intervention Description: Peer educators are themselves PLWHA on ART who have demonstrated good ART adherence for at least 6 months. Selection criteria include having a minimum of Primary 7 grade education and demonstrated literacy. Peer educators are nominated by their fellow patients at each clinic, approved by the field staff, and receive basic training on their roles and responsibilities. The peer educators are responsible for ~15-20 patients and are expected to visit the patients in their homes once every two weeks. At these visits, peer educators record a review of symptoms, client self-report of adherence, and a pill count. At the clinic, peer educators assist with patient organization and share their experiences, particularly with patients about to start ART. Peer educators undergo an initial, intensive two day residential training course and are provided with a bike and basic supplies, and a modest amount of remuneration to encourage compliance with their responsibilities and promote a high program retention rate.

Please note, Peer Educators are staff performing routine care functions, so no consent it required. Only de-identified data will be analyzed by community of randomization

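### Time on ART is not named in the baseline comparison or as a covariate, and the continuous outcomes have no covariate adjustment, so the analysis gives up some precision and protection against chance imbalance.

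*Protocol*

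**What the plan says.** Under Power Calculations or Statistical Plan, the protocol compares arms at enrollment "with respect to sociodemographic characteristics, WHO stage, viral load, CD4 count and Karnofsky score". Dichotomous outcomes go to log-binomial regression with GEE robust variances, "adjusted for covariates found to differ between arms at p < 0.15 in univariate analyses, or suspected confounders". That sentence mentions adherence alongside treatment failure. Adherence percent, CD4 change and the number of toxicity events are then assigned to tests and ANOVA, and no covariates are mentioned.

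On who is in the cohort, Gender, Age and Locale states: "In June 2004, with PEPFAR funding, antiretroviral therapy was provided through a community-based mobile clinic program operating in 15 localities". It adds: "The program has ~1000 active patients on ART with ongoing recruitment". Recruitment Process states: "Population will be ~1000 PEPFAR patients enrolled in the RHSP ART program by March, 2007". Sample Size puts the date at May 2007 and says that about 800 of about 1000 patients already have about 6 months of pilot follow-up. Inclusion requires only receipt of ARVs. Virologic failure is a viral load above 400 copies/ml, with no minimum time on treatment.

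Data Collection schedules "CD4 counts every three months for one year, and then every six months thereafter", and questionnaires from ART initiation, "weekly for the first month, and then at 3, 6, 9, 12, and 24 months on ART".

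**The concern.** Time on ART plausibly affects both whether viral load is still detectable and how far CD4 has risen. The programme's denser CD4 schedule in the first year fits that expectation. A variable that is not in the list compared between arms is not sure to reach the p < 0.15 screen. The only other way in is a clause that names no variable and sits in the sentence on dichotomous outcomes.

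The continuous outcomes do not have even that route. If baseline means ART start, CD4 change sets a few months of recovery in some patients beside several years in others. If it means study entry, enrollment viral load and CD4 carry part of the information on time treated, but only part. The protocol does not say which is meant.

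At stake is a difference in clinic mix that arises by chance among 15 clinics and is left in the estimate, together with between-clinic variation that a known covariate could partly remove.

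**Working it through.** **Figures in the plan.** The protocol gives none for this point. Its person-time reproduces: 330 × 18 × 0.95 = 5,643 months, or 470 person-years. Its 80% power at RR 0.70 does not: 330 per arm with design effect 1.26 gives 62%. That is a separate problem and does not decide this one. Inputs taken from the protocol are 28% failure in control, 19.6% under the target effect (a gap of 8.4 points), k = 0.24, and 6, 4 and 5 clinics.

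**Range of time on ART.** June 2004 to March 2007 is 33 months, and to May 2007 it is 35. About 1000 − 800 = 200 patients (20%) have less than the pilot follow-up or none. This fits a sizeable share of recent starters but does not establish one.

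**Assumptions (not in the documents).** δ is the gap in failure risk between recent and established patients, taken as 0.10 to 0.40. With 20% recent starters, a failure ratio of 2 implies an established risk of 0.28/1.2 = 0.233 and so δ = 0.23. A ratio of 3 implies 0.28/1.4 = 0.20 and δ = 0.40. s is the clinic-to-clinic SD of the recent-starter share, taken as 10 points unless stated.

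**Chance imbalance in the share.** SD of the arm difference = s × √(1/c₁ + 1/c₂).
- Control v phone arm: 10 × √(1/5 + 1/4) = 6.7 points
- Control v both peer-educator arms: 10 × √(1/5 + 1/10) = 5.5 points

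A difference of 10 points or more in either direction then occurs in about 14% and 7% of randomisations.

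**Effect on the failure comparison.** Spurious RR = 1 − δ × (share difference)/0.28 when the intervention arm has fewer recent starters.
- 10 points: 1 − 0.10 × 0.10/0.28 = 0.96, to 1 − 0.40 × 0.10/0.28 = 0.86
- Share difference that would copy the whole target effect, 0.084/δ: 84, 42, 28 and 21 points at δ = 0.1, 0.2, 0.3 and 0.4
- 95% chance range of the risk difference, control v phone arm, 1.96 × δ × 6.7: ±1.3 points (δ = 0.1) to ±5.3 points (δ = 0.4)

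**Precision recoverable by adjustment.** Mix alone contributes k_mix = δs/0.28. Take this as part of k = 0.24, so that adjustment leaves k² = 0.24² − k_mix². With 66 patients per clinic, each arm contributes [p(1 − p)/66 + k²p²]/c to the variance of the risk difference. For control v phone arm at RR 0.70 without adjustment, the variance is 0.00757/5 + 0.00460/4 = 0.00266. The z-value is 0.084/0.0516 − 1.96 = −0.33, and power is 37%.

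| δ | k_mix | share of k² | power, unadjusted to adjusted |
|---|---|---|---|
| 0.1 | 0.036 | 2% | 37.0% to 37.3% |
| 0.2 | 0.071 | 9% | 37.0% to 38.5% |
| 0.4 | 0.143 | 35% | 37.0% to 44.1% |

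If the mix came on top of k = 0.24 instead, the same three cases would lower unadjusted power to 36.6%, 35.5% and 31.9%.

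A simulation of both peer-educator arms v control (8,000 trials per scenario, 67 patients per clinic, total k held at 0.24, t-test on clinic log ratios with 12 df) gave 0.40 to 0.41 in the weakest scenario and 0.42 to 0.50 at ratio 3 and s = 10. It gave 0.45 to 0.66 at ratio 3 and s = 15, but there k_mix = 0.40 × 0.15/0.28 = 0.214, about 80% of k². Nothing in the protocol supports so large a share.

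**CD4 change.** Assume an extra first-year gain of 60 to 100 cells, patient SD 120, ICC 0.02 and an effect of 40 cells. A 10-point imbalance adds 0.10 × 60 = 6 to 0.10 × 100 = 10 cells. Simulated power at s = 10 rises from 0.82 to 0.85 (gain 60) and from 0.76 to 0.85 (gain 100).

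**Why the screen is not enough.** At a 20% share with 330 per arm and clustering ignored, SE = √(2 × 0.2 × 0.8/330) = 0.031. A 5-point difference passes p < 0.15 about 57% of the time, and a 10-point difference about 96%. Both figures presuppose that the variable is tested at all.

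**The case against.** The strongest reply is that the adjustment list is open. The suspected-confounders clause needs no p-value and can admit time on ART. It sits in a sentence that covers adherence as well as failure, and naming each confounder is often left to an analysis plan, which is not shown here. This stands against any claim that the protocol excludes time on ART. It does not help adherence percent or CD4 change, for which the protocol itself fixes tests and ANOVA. Nor does it explain a comparison list that the protocol wrote out without this variable.

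The list of descriptive data under Data Collection is no evidence of exclusion either. It also omits viral load and CD4, which the statistical plan does compare.

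A reader might infer that the trial is biased. The documents do not support that: clinics are randomised, so the imbalance is chance, and cluster-robust variance is meant to reflect it. A raised false-positive rate (up to 12% in simulation) applies only conditional on a chosen imbalance. A reader might also infer that the planned power is overstated for this reason, but the variation may already lie inside k = 0.24.

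Finally, viral loads are six-monthly and a further year of follow-up is planned, so few outcome values should come from the first weeks of treatment. That is fair and argues for the lower end of the range.

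**Conclusion.** The point holds in a limited form. Time on ART is not named in the baseline comparison, reaches the log-binomial models only at the analysts' discretion, and has no stated route into the analysis of adherence percent or CD4 change. The cohort spans new starters to about 33-35 months on treatment, with 4 to 6 clinics per arm.

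The cost is avoidable imprecision and exposure to chance imbalance. No figure in the protocol changes. Under the stated assumptions, a 10-point imbalance moves the risk ratio by 0.04 to 0.14, and adjustment gains between less than one and about seven points of power for control v phone arm at s = 10. δ, s, the share of recent starters and all the CD4 inputs are assumptions, so the size can be stated only as trivial to moderate. The case for the change rests on its low cost.

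**What to change.** In Power Calculations or Statistical Plan:

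- Add time on ART at study entry to the baseline comparison. Study entry is the start of intervention exposure, and the value is zero for patients who start ART later.
- Enter it as a pre-specified covariate, whatever its p-value, in the cluster-adjusted models for virologic failure, adherence, CD4 change, opportunistic infection or toxicity, and mortality.
- Replace the unadjusted ANOVA for continuous outcomes with a covariate-adjusted model that allows for clustering.
- State whether enrollment and baseline mean ART start or study entry.

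The value should be fixed at entry, not taken at the outcome measurement. For mortality, time on ART at outcome depends on when the patient died. After a further year of follow-up, the shortest bands would also be nearly empty.

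Derive the variable before de-identification, because under Description of Measures to Minimize Risks the analysts receive only a stripped data set with no linkage. The ART start date should already be held, since questionnaires are timed from it. The cost is one more abstracted variable, a few lines of text and a few patient-level degrees of freedom.
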